# 6.2.2 Secondary endpoint (clinical status):

We will evaluate the clinical efficacy of CCP relative to the control arm in adults hospitalized with COVID-19 according to clinical status (8-point WHO ordinal scale) using a proportional odds model. Because clinical status is evaluated on multiple days, we will use a generalized estimating equations (GEE) approach to account for repeated measures within each patient. Changes in ordinal scale at each timepoint will be summarized by proportions.

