# 4.1.4 **Target population**

This study will enroll hypoxic hospitalized COVID-19 patients, a group that is at elevated risk for poor outcomes and progressive respiratory failure. To date, approximately 30-50% of hospitalized San Francisco COVID-19 patients have required intensive care level treatment, the majority due to respiratory failure[1]. This high progression to ICU level care due to respiratory failure has been seen across the US. This study targets patients who are still early in the course of disease, when CCP may be most effective, the "green zone" described in Figure 2. Once severe respiratory decompensation and ARDS occur and patients have progressed to the "red zone", CCP may be less effective, as was the case with use of CCP in SARS-1 -[8]. The study has been amended to include those on high flow nasal oxygenation, as well as those on nasal cannula. In the ACTT-1 study, 25% of participants on HFNC (ordinal group 6) progressed to mechanical ventilation or death [22] These individuals are at elevated risk of progression to intubation and it is important to understand if CCP can reduce deterioration of respiratory status.

This study will permit enrollment of pregnant women, breastfeeding women and women of childbearing potential. CCP should not pose a pregnancy specific risk, other than the known risks associated with blood product infusions in general. However, for pregnant or breastfeeding women, additional counseling will be provide as to the lack of data for CCP use in COVID-19 infection during pregnancy and lactation and that an adverse event that impacts the participant could also affect an unborn child by affecting maternal health. Pregnant women who chose to enroll will have the pregnancy outcome recorded.

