# 5.3.5 **Randomization:**

1. Subjects enrolled in the study will be randomized using a web based randomization procedure to receive convalescent plasma versus non-immune plasma at a 1:1 ratio.

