# 6 STATISTICAL PLAN

#### 6.1 Sample Size and Power Considerations

All power calculations were performed using Stata "power" package assuming a two-tailed  $\alpha$ =0.05. The planned sample size for the trial is 50 subjects, randomized in a 1:1 ratio to anti-SARS-CoV-2 convalescent plasma versus control plasma. The primary analysis will compare the combined endpoint of mechanical ventilation or death in the anti-SARS-CoV-2 convalescent plasma and control groups.

We base our sample size projection on the ACTT-1 data [22]They reported the progression within 15 days separately for COVID-19 hospitalized requiring supplemental oxygen and those requiring high flow oxygen or non-invasive ventilation. The proportion progressing were 20% and 34%, respectively in the standard of care group and 8% and 25% in the remdesivir group progression. For our assumption we assume a 32% progression rate on the standard of care (no convalescent plasma) In the absence of treatment with convalescent plasma, we anticipate that between 10 to 30% will experience the primary outcome of mechanical ventilation or death . Using the Fisher exact test: we will reject the null hypothesis under the data scenario in the Table below.

No. Mechanical ventilation/Death (%)	Control arm (%)	Active arm (%)
	5/25 (20%)	0/25 (0%)
	6/25 (24%)	<= 1/25 (4%)
	7/25 (28%)	<= 1/25 (4%)
	8/25 (32%)	<= 1/25 (4%)
	9/25 (36%)	<= 2/25 (8%)
	10/25 (40%)	<= 3/25 (12%)

Rejection Region for the Fisher Exact Test

We will use an 8-point ordinal scale to assess clinical status, based on WHO clinical trial guidance. We assume the same distribution of outcomes for the control arm (i.e., in the absence of treatment with

convalescent plasma) as in ACTT, as tabulated below. Assuming 25 participants are treated with convalescent plasma and 25 participants are untreated, we would have 80% power to detect a difference between treatment arms as follows:

Category	Control arm (%)	Active arm (%)
Death	12%	0
Hospitalized, on invasive mechanical ventilation plus additional organ support (pressors, RRT, ECMO)	0	0
Hospitalized, intubated and mechanical ventilation	20.0%	0
Hospitalized, on non-invasive ventilation or high flow oxygen devices;	12%	8%
Hospitalized, requiring supplemental oxygen fy mask or nasal prong	0	20%
Hospitalized, not requiring supplemental oxygen – requiring ongoing medical care (COVID-19 related or otherwise);	24%	12%
Not hospitalized, limitation on activities	16%	28%

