# 6.2 Statistical Analysis

# 6.2.1 **Primary endpoint**

Our primary hypothesis is that by providing anti-SARS-CoV-2 plasma, the rate of progression to mechanical ventilation or death will be decreased as compared to the rate in in the group receiving control plasma. We will apply a Fisher exact test to compare the combined endpoint of mechanical ventilation/death respiratory failure rates between the two groups occurring by day 15. 29. All analyses

will be conducted with a modified intention-to-treat approach, which excludes randomized subjects who do not initiate an infusion of the study plasma. As secondary analysis, we will also analyze the reduced oxygenation rate, requirement for supplemental oxygen rate, length of hospitalization, time to recovery (ordinal score 1-3) and mechanical ventilation rate, respectively, as well as occurrence of the primary endpoint by day 29 Statistical inference will be based on a two-sided Type 1 error rate of 0.05 and 95% confidence intervals.

Participants who are intubated for reasons other than hypercarbia/hypoxia, such as for a procedure or airway obstruction, will have ventilation settings evaluated to determine if need for ventilation due to hypoxia is meet. This will be determined by >12 hours of requirement for a mandatory mode of ventilation (volume control or pressure control) or Fi02 of > 40%. External adjudication of intubation for non-hypoxic/hypercarbic indication will be conducted.

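### The ordinal model for the key secondary endpoint names no baseline covariate, although baseline oxygen support is prognostic in the plan's own cited figures and is already recorded

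*Combined protocol and SAP*

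**What the plan says.** Section 6.2.2 analyses the 8-point clinical status scale "using a proportional odds model" and uses GEE because each patient is scored on several days. No covariate is named. Changes on the scale are to be summarised as proportions, which is not an adjustment for the starting score. Section 5.1 makes Day 29 clinical status the key secondary objective.

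On the population, Section 4.1.4 says: "The study has been amended to include those on high flow nasal oxygenation, as well as those on nasal cannula". Section 6.1 cites the earlier remdesivir trial by the same split, supplemental oxygen first and high flow or non-invasive ventilation second: "The proportion progressing were 20% and 34%, respectively in the standard of care group and 8% and 25% in the remdesivir group".

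On allocation, Section 5.3.5 says only: "Subjects enrolled in the study will be randomized using a web based randomization procedure", at 1:1. It names no stratification factor, block or minimisation. The primary test in 6.2.1 is an unstratified Fisher exact test.

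The Schedule of Evaluations and the day-by-day procedures in Section 5.4 record route of oxygen support at baseline and the 8-point score at enrolment (Day 1).

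**The concern.** The plan uses rates split by baseline oxygen support to set its assumptions, and then does not carry that factor into the analysis. In a trial of 50, the two arms can easily differ in their mix of low-flow and high-flow patients. If they do, an unadjusted ordinal odds ratio is pulled away from the treatment effect by an amount that could have been removed with data already in hand. Even with balanced arms, leaving out a prognostic covariate costs some power. At stake is how well the key secondary endpoint can show an effect. If the covariate is not named in advance, adding it after unblinding would carry little weight.

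**Working it through.** **Inputs from the documents.** 25 patients per arm, 1:1 (6.1). Inference at "Statistical inference will be based on a two-sided Type 1 error rate of 0.05" (6.2.1). Progression of 20% vs 34% and 8% vs 25% by oxygen support, and the control-arm category distribution tabulated in 6.1.

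**Inputs assumed.** The high-flow share is not given. 50% is used, with 30% and 70% as a range, and 86% as the value implied by the plan's 32% control rate: (32 − 20)/(34 − 20) = 0.857. The cited rates concern ventilation or death; using their odds ratios for the whole ordinal scale is an assumption.

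**1. The plan's own figure.** Section 6.1 says "we would have 80% power to detect a difference between treatment arms as follows". By Whitehead's formula, power = Φ(ln OR × √[N(1 − Σp̄³)/12] − 1.96). With N = 50, the fitted common OR of 3.51 and Σp̄³ = 0.0335 from the averaged columns, this is Φ(1.255 × 2.007 − 1.96) = Φ(0.559) = 71%. Simulation gives 70% (proportional odds likelihood-ratio test) and 68% (Wilcoxon). The stated 80% is not reproduced at two-sided 0.05. It appears at one-sided 0.05 (80.6% for the likelihood-ratio test). That is a separate matter, but it means there is little power to spare.

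**2. Prognostic strength.**
- Standard of care: (0.34/0.66)/(0.20/0.80) = 2.06; difference 14 points.
- Remdesivir: (0.25/0.75)/(0.08/0.92) = 3.83; difference 17 points.

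**3. Chance imbalance.** Under simple randomisation, the number on high flow in each arm is binomial(25, share). The probability that the arms differ by 5 or more of 25 (20 points), in either direction, is:

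| High-flow share | Probability |
|---|---|
| 30% or 70% | 16% |
| 50% | 20% |
| 86% | 7% |

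Imbalance against the active arm alone is half of each figure, so 10% at a 50% share. A 20-point imbalance shifts the expected difference between arms in ventilation or death by 0.20 × 14 = 2.8 to 0.20 × 17 = 3.4 points. That is 25 × 0.028 = 0.70 to 25 × 0.034 = 0.85 of one event.

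**4. Power with and without the covariate.** Single-time-point proportional odds likelihood-ratio tests, simple randomisation, control distribution from 6.1, treatment OR 4.0, 1,500 simulated trials per scenario (Monte Carlo standard error about 1 point):

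| Share | Baseline OR | Unadjusted | Adjusted | Gain |
|---|---|---|---|---|
| 30% | 2.06 | 78.1% | 79.1% | 1.0 |
| 50% | 2.06 | 76.3% | 77.6% | 1.3 |
| 70% | 2.06 | 77.3% | 78.3% | 1.0 |
| 30% | 3.83 | 73.5% | 78.9% | 5.4 |
| 50% | 3.83 | 72.5% | 77.3% | 4.8 |
| 70% | 3.83 | 73.5% | 79.1% | 5.6 |

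**5. The unlucky trial.** At a 50% share, about 10% of simulated trials gave the active arm 5 or more extra high-flow patients (standard error within this subset about 4 points):
- Baseline OR 2.06: power 62% unadjusted, 71% adjusted (gain 9). Median estimated OR 3.3 against 4.3; true value 4.0.
- Baseline OR 3.83: power 47% unadjusted, 74% adjusted (gain 27). Median estimated OR 2.6 against 4.1.

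**6. Type I error and stratification.** With no treatment effect, the unadjusted test rejects in 4.8% (OR 2.06) and 5.0% (OR 3.83) of trials. Stratified randomisation plus adjustment gives power of 79% and 78%, against 78% and 77% for adjustment alone, which is within simulation error. Stratification without adjustment gives 76% and 70%, with type I error of 4.3% and 3.3%.

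**The case against.** The plan is silent; it does not rule adjustment out. A reader might infer that allocation is stated to be unstratified and that the model is stated to contain treatment alone. Neither statement appears, so the supportable claim is that no factor and no covariate are specified. That still leaves a gap in the analysis plan.

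A reader might also infer that imbalance makes the unadjusted result invalid or could readily produce a false finding. The numbers do not support this: overall type I error is sound. On the primary endpoint, a 20-point imbalance moves the contrast by less than one event, while the rejection table in 6.1 shows gaps of 5 to 7 events.

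The probability of imbalance can be made to look larger. With arms of exactly 25 and exactly 25 of 50 patients on high flow, it is 26%. Nothing in the documents fixes that mix. The plan's 32% control rate points to a share near 86%, where the figure is 7%. Section 6.1 also anticipates 10% to 30%, and the eligibility steps in Section 5.4 rule out patients already in intensive care, so the share is open.

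The simulations model one time point, whereas 6.2.2 plans GEE over several days, so the power figures are a guide to the planned analysis and not a direct measure of it. That limit stands.

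Finally, a reader might infer that randomisation must be stratified. Once the model is adjusted, stratification adds almost nothing here, and it would be a change during the trial.

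**Conclusion.** The point holds as one about precision and robustness, not validity. The planned model for the key secondary endpoint names no baseline covariate, the plan's own cited rates show baseline oxygen support to be prognostic, and the variable is already recorded. At the cited odds ratios, adjustment is worth about 1 to 6 points of power on average for shares of 30% to 70%. It is worth about 9 to 27 points in the roughly one trial in ten, at a 50% share, where the active arm draws 5 or more extra high-flow patients. These sizes rest on an assumed high-flow share, on carrying odds ratios for ventilation or death over to the whole scale, on a treatment OR of 4.0, and on a single-time-point model. The average gain is modest. The case for the change is that it costs almost nothing and protects a trial that will be run only once.

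**What to change.** - In 6.2.2, prespecify that the proportional odds GEE model includes baseline oxygen support as a covariate. Define it from the Day 1 ordinal score before infusion, in two groups: no oxygen or low-flow oxygen (scores 3 and 4 on the WHO scale in Section 5.4) against high flow or non-invasive ventilation (score 5). The lower group must include patients on no oxygen, because saturation below 95% on room air qualifies a patient without requiring supplemental oxygen.
- State that only post-baseline days enter as outcomes, so that Day 1 is not used both as covariate and as response.
- In 6.2.1, keep the Fisher exact test as primary and add an exact test stratified by the same two groups as a sensitivity analysis.
- Optionally, stratify the remaining randomisation in 5.3.5 by the same grouping, but only together with the adjusted model.

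The first three changes cost SAP wording, agreed before unblinding, and need no new data. The optional one needs a protocol amendment and a randomisation system that supports it, which the documents do not describe.

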# 6.2.3 Other secondary endpoints:

Differences in time-to-event endpoints (e.g., death, hospital discharge) will be summarized by treatment arm using Kaplan-Meier curves and 95% confidence bounds. Duration of events (e.g., days of hospitalization, supplemental oxygen, ventilation) will be summarized by treatment arm by median days with quartiles. Binary data (e.g., incidence of new oxygen use) will be summarized by treatment arm as percentages with 95% confidence intervals. Categorical data (e.g., 29-day mortality, ordinal scale by day) will be summarized by treatment arm as proportions by category and using odds ratios with 95% confidence intervals.

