
 
Invasive Mechanical Ventilation / extracorporeal membrane oxygenation (ECMO):
 
Ventilator / ECMO use up to Day 29.
 
Incidence and duration of new mechanical ventilation or ECMO use during the study.
 
	
 
Days of invasive mechanical ventilation/ECMO (if applicable) up to Day 29.
 

 
Hospitalization
 
Duration of hospitalization (days).
 
	
 
Days of hospitalization as of Day 29 and day 120
 

Mortality 
 
15-day mortality
 
29-day mortality
 
120-day mortality
 
	
 
Date and cause of death (if applicable)
 

To evaluate the safety of CCP as compared to the control arm as assessed by:	• SAEs

 
Cumulative incidence of SAEs through Day 29.
 
Cumulative incidence of Grade 3 and 4 clinical and/or laboratory AEs through Day 29.
 
Transfusion associated adverse events
 
	
 
Grade 3 and 4 AEs
 
Grade 2 or higher AE's attributed to CCP
 

 
Exploratory Objectives
 
To evaluate the virologic efficacy of CCP
 
	

 
as compared to the control arm as assessed by:
 
Percent of subjects with SARS-CoV-2 detectable in nasal sample at Days 1,5,8,15
 
Quantitative SARS-CoV-2 virus in NP/MTN sample at Days 1,2,5,8,15
 
	
 
Qualitative and quantitative polymerase chain reaction (PCR) for SARS-CoV-2 in NP/MTN swab on Day 1,2,5,8,15 (while hospitalized)
 

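### The plan does not say how patients who die enter the discharge, recovery and duration summaries; the usual defaults would overstate discharge and recovery in the arm with more deaths

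*Combined protocol and SAP*

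**What the plan says.** Section 6.2.3 names the methods. For event times: "Differences in time-to-event endpoints (e.g., death, hospital discharge) will be summarized by treatment arm using Kaplan-Meier curves and 95% confidence bounds". For durations: "Duration of events (e.g., days of hospitalization, supplemental oxygen, ventilation) will be summarized by treatment arm by median days with quartiles".

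The endpoint tables in Sections 3 and 5.1 define the durations as plain day counts. Examples are "Days of hospitalization as of Day 29 and day 120" and "Days of invasive mechanical ventilation/ECMO (if applicable) up to Day 29". They are not days alive and free of the state.

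Section 6.2.1 lists further secondary analyses, among them "length of hospitalization, time to recovery (ordinal score 1-3) and mechanical ventilation rate, respectively". The next statement is "Statistical inference will be based on a two-sided Type 1 error rate of 0.05 and 95% confidence intervals", but no test is named for these outcomes.

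No section gives a censoring rule, a competing-event method, a value for patients who die, or a free-days endpoint. Death is counted elsewhere: in the primary composite, as the worst category of the ordinal scale, and as mortality at Days 15, 29 and 120. Section 6.2.7 compares in-hospital and 29-day mortality by the primary method.

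**The concern.** Death ends hospitalization, oxygen use and ventilation, and it rules out later discharge or recovery. The documents put death and discharge in the same Kaplan-Meier sentence without noting that one precludes the other.

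With no rule, an analyst will probably follow the software default. For discharge or recovery that means censoring at death, which treats a dead patient as someone who could still go home. For day counts it means stopping the count at death, so an early death enters as a short stay or a short spell of ventilation.

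If plasma reduced mortality, these outputs would make the control arm look better on discharge and recovery than it was, and possibly on durations too. Silence also leaves the choice open until the data have been seen. Section 4.1.9 says the data will be pooled with similar trials, which needs explicit definitions.

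**Working it through.** The plan states no figure for these analyses, so there is none to reproduce. The check uses the plan's own outcome table.

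**Inputs from Section 6.1, 25 per arm**
- Control: dead 12% (3/25); not hospitalized 16% + 16% = 32% (8/25); still in hospital 100% − 12% − 32% = 56% (14/25).
- Active: dead 0%; not hospitalized 28% + 32% = 60%.
- Assumptions: the table does not name a day, so I read it as status at Day 29. I take everyone not hospitalized as discharged once, with no other loss to follow-up.

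**Discharge curve, control arm.** Let F = 0.32 be the proportion discharged and d = 0.12 the proportion dead.
- Deaths kept as never discharged (equal to the cumulative incidence here): 8/25 = 32.0%.
- Deaths censored, all before any discharge: 1 − KM = F/(1 − d) = 0.32/0.88 = 36.4%. In counts, 1 − 14/22 = 36.4%.
- Deaths censored, constant hazards: the total cumulative hazard is −ln(1 − 0.44) = 0.580. The discharge share is 0.580 × 0.32/0.44 = 0.422, so 1 − exp(−0.422) = 34.4%.
- Deaths censored, all after the last discharge: 32.0%, no bias.

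The active arm has no deaths, so its 60% does not change.

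| Handling of control deaths | Control | Gap |
|---|---|---|
| Never discharged | 32.0% | 28.0 points |
| Censored, constant hazards | 34.4% | 25.6 points |
| Censored, all deaths first | 36.4% | 23.6 points |

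The bias grows with mortality. At an assumed 60% discharged and 25% dead, censoring gives 73.8% (constant hazards) to 80.0% (0.60/0.75), an overstatement of about 14 to 20 points.

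**Length of stay, same table.** Counting death as the end of stay raises the share of stays ended by Day 29 from 8/25 (32%) to 11/25 (44%). Both are below half, so the control median is at the Day 29 cap either way. Only the first quartile can move.

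**Length of stay, assumed general case.** Log-normal stays with survivor median 10 days, 12% mortality, capped at Day 29 (log-SD 0.7 for stays, 0.6 for death times):

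| Handling of deaths | Median stay |
|---|---|
| No deaths | 10.0 days |
| Counted to death, median death day 5 | 9.2 days |
| Counted to death, median death day 10 | 10.0 days |
| Counted to death, median death day 20 | 10.9 days |
| Deaths set to 29 days | 11.3 days |

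The direction therefore depends on when the deaths occur.

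**Ventilator days among the ventilated.** All inputs on timing are assumed, and every death is treated as a ventilated patient: 12 of 32 die, survivor median 12 days, log-SD 0.6. Counting days to death gives a median of 8.3 days (median death day 4), 9.3 (day 6) or 12.0 (day 12), against 12.0 with no deaths and about 20 with deaths set to 29. With a survivor median of 14 days, the figures are 9.3, 10.4, 12.4, 14.0 and 16.0 for median death days 4, 6, 10, 14 and 20.

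**The case against.** The strongest reply is that the documents show a missing rule and not a wrong one. That stands. A reader might infer that the plan prescribes censoring at death, or scores death as a short stay. It does neither. A Kaplan-Meier curve that holds deaths in the risk set to Day 29 as never discharged would fit the text and, with no other censoring, would equal the cumulative incidence.

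A reader might also infer that these summaries would point the wrong way. On the plan's own table they do not: the gap keeps its sign and remains at least 23.6 points. Nor does the arm with more deaths always look better on durations, since late deaths lengthen them.

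The 12% against 0% mortality should not be read as a forecast. The control column is an assumption, but the active column is the difference said to be detectable with 80% power. The ventilator figures show sensitivity only. The table does not say that the dead were ventilated, and its active column has nobody ventilated or dead, so there is no active median to compare.

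Finally, mortality is reported separately, Section 6.2.3 describes summaries only, and the trial is a 50-patient proof of concept. This protects the primary and key secondary conclusions. It does not tell a reader of the discharge, recovery or ventilation results how the deaths were counted.

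**Conclusion.** The point holds as a gap in specification with a foreseeable bias under the usual defaults. On the Section 6.1 table, censoring deaths overstates control discharge by 0 to 4.4 points (2.4 under constant hazards), and the gap between arms falls from 28 points to as little as 23.6. The control median stay does not move. In that scenario the excess deaths are in the control arm, so the bias would run against plasma. The size rests on reading the table as Day 29 status and on the order of deaths and discharges. Effects on ventilator days and on stay in general depend on death times that the documents do not give. The primary composite, the ordinal scale and the mortality comparisons are unaffected.

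**What to change.** In Section 6.2.3, and for time to recovery in Section 6.2.1:

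- Estimate discharge and recovery by cumulative incidence (Aalen-Johansen) with death as a competing event. Equivalently, when there is no other loss to follow-up, hold patients who die as not discharged or recovered through Day 29.
- Keep Kaplan-Meier for death.
- Report hospital-, oxygen- and ventilator-free days to Day 29, with patients who die given the worst value (0 free days), alongside the raw medians. Say how deaths enter those medians, and state the rule for the Day 120 hospital-day count as well.

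The endpoint tables already call for the date of death, daily clinical status in hospital and the day counts, so no new data are needed. The cost is a few SAP sentences and standard code. The downside is that free days become another composite that includes death, beside the primary endpoint and the ordinal scale. Showing the raw medians next to them keeps the components visible.
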